## 9. Sample size calculation

The sample size calculation of RoC-HF is based on data from previous analyses that reported prevalence data of osteoporosis among patients with HFrEF leading to an expected prevalence of osteoporosis in RoC-HF of 20%. Osteoporosis is defined as a T-Score < -2.5 (measured by DXA), and severe osteoporosis is defined as a T-Score < -2.5 and presence of a fragility fracture, e.g., a vertebral fracture. In most of available studies on patients with HFrEF, data from DXA scans were not available. Therefore, presence of a vertebral fracture was commonly used as a criterion of osteoporosis. Thus, these studies likely underestimated the real prevalence of osteoporosis, because presence of a fracture may constitute only the "tip of the iceberg". Taken together, previous studies reported on prevalences of osteoporosis of 12 – 16% (see **Table 6**).

Table 6: Prevalence of osteoporosis as reported in previous heart failure cohorts				
Study	Patient number	Heart failure definition	LVEF in %	Data
Lyons et al (30)	623	Listed for transplant	32 +/- 16	12% with vertebral fractures
Mazziotti et al (31)	1031 (430 vs 601 healthy controls)	ICD + revision of clinical records	27 (15-45)	16.1% with vertebral fracture
Youn et al (32)	65	Acute decompensated heart failure	28 +/- 12 (males) 36 +/- 16 (females)	15% with T-Score < -2.5

Given that the RoC-HF study procedures comprise DXA scan as well as X-ray of both the thoracic and lumbar spine, we expect a prevalence of osteoporosis in RoC-HF of 20 % (95% confidence interval: 14 -26). Calculating with a significance level of 5% and a two-sided P-value leads to a number of 171

participants to be analyzed. Calculating with 20% unavailable data due to invalid ABPM, missing laboratory values or other missing parameters, we will need to enroll 205 subjects in total.

Support in sample size calculation was provided by the Institute for Medical Informatics, Statistics and Documentation of the Medical University of Graz ([name]).

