## 10. Statistical analyses

Data will be illustrated by descriptive statistics using numbers and percentages for categorical variables and means and standard deviation or medians and interquartile range for continuous variables, respectively, as appropriate.

To test our primary hypotheses, the correlation between a bone formation marker or central arterial systolic pressure (independent variable, respectively) with LV systolic function (dependent variable) will be analyzed using multivariate linear regression analyses, with adjustment for age, sex, blood lipids, blood glucose, kidney function and other potentially confounding variables.

Differences of echocardiographic and other variables between patients with and without osteoporosis or other categorical variables will be compared using student's t-test, Mann-Whitney U test or analysis of variance (ANOVA), as appropriate. These differences will also be analyzed using multivariate analyses of covariance (ANCOVA), with osteoporosis (yes/no) as fixed factor, echocardiographic or other continuous variables dependent variable and age, sex, blood pressure, blood lipids, blood glucose, kidney function and other potentially confounding variables as covariates. Also other categorical variables of interest and their association with continuous outcome variables will be analyzed in the same manner.

Statistical analyses of the RoC-HF study will be the responsibility of the PIs or persons who received the permission by the PIs to perform statistical analyses. The PIs have published more than 15 original manuscripts in the field of epidemiological research, partly as first authors, and have thus proven their expertise to conduct statistical analyses. Support in statistical analyses will also be provided by [name] or PD [name] who have authored more than 100 peer-reviewed original manuscripts in the field of epidemiological research.

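### DXA bone density is related to cardiac and other variables only as osteoporosis yes/no; a continuous T-score or BMD term should be added alongside

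*Combined protocol and SAP*

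**What the plan says.** Section 9 gives the definition: "Osteoporosis is defined as a T-Score < -2.5 (measured by DXA". It names no skeletal site.

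Section 10 then uses the diagnosis in two ways. Unadjusted differences "between patients with and without osteoporosis or other categorical variables will be compared using student's t-test", the Mann-Whitney U test or ANOVA, as appropriate. The adjusted analysis is an ANCOVA "with osteoporosis (yes/no) as fixed factor, echocardiographic or other continuous variables dependent variable", with age, sex, blood pressure, lipids, glucose, kidney function and other possible confounders as covariates. Other categorical variables may be handled in the same way.

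The same section also plans a linear regression of LV systolic function on a bone formation marker or on central systolic pressure, and calls this the test of the primary hypotheses. No categorisation of the marker is stated.

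Under DXA-scan in section 6d, the lumbar spine, femoral neck and distal radius are scanned, together with a full-body scan. A graded density measurement will therefore exist for every patient scanned. No section plans to use it as a continuous predictor.

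**The concern.** The yes/no coding places a patient at T = -2.4 with one at +1 and separates that patient from one at -2.6. If cardiac function changes gradually with bone density, most of that gradient is lost within the two groups.

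This bears on what the study sets out to do. Section 2 criticises earlier heart failure studies for lacking baseline bone mineral density, and it names bone metabolism and bone status as separate things. Section 4 promises to examine the link between bone disease and cardiac function. The marker regression covers turnover. For density, the only planned analysis is the coarse one.

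What is at stake is precision and power for exploratory associations. No planned estimate becomes biased, and the validity of the prevalence result is not in question.

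**Working it through.** **Inputs.** From section 9: "we expect a prevalence of osteoporosis in RoC-HF of 20 % (95% confidence interval: 14 -26"; two-sided 5% significance; 171 analysed. Assumptions, because the documents give no figure: a roughly normal T-score, a linear relation with the cardiac variable, the correlations used for power, and any difference in SD between groups. The power figures are unadjusted and approximate.

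**1. The plan's own figure.** n = 1.96² × p(1−p)/h² with p = 0.20 and h = 0.06 gives 170.7, rounded up to 171. The stated number is reproduced. It is a precision calculation for a prevalence; no effect size or power is stated for the cardiac comparisons.

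**2. Information kept by the split.** For a normal predictor cut at its p-th quantile, efficiency relative to a linear term is φ(z_p)²/[p(1−p)]. At p = 0.20, z = −0.842 and φ = 0.280, so the correlation is multiplied by 0.280/√0.16 = 0.700 and the efficiency is 0.700² = 0.490.

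| Share below cut | Efficiency | Loss | 171 act like |
|---|---|---|---|
| 14% | 0.411 | 59% | 70 |
| 20% | 0.490 | 51% | 84 |
| 26% | 0.547 | 45% | 94 |

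**3. Power at n = 171.** Fisher z: Φ(atanh(r) × √168 − 1.96), with √168 = 12.96.

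- r = 0.20, continuous: 0.2027 × 12.96 − 1.96 = 0.67, power about 75%. Split, r = 0.140: 0.1409 × 12.96 − 1.96 = −0.13, power about 45%.
- r = 0.25, continuous: 0.2554 × 12.96 − 1.96 = 1.35, power 91%. Split, r = 0.175: 0.1768 × 12.96 − 1.96 = 0.33, power 63%.
- The smallest correlation detectable with 80% power rises from 0.213 to 0.213/0.700 = 0.304.
- As a group difference, with 0.20 × 171 ≈ 34 against 137: 2.80 × √(1/34 + 1/137) = 0.54 SD.

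**4. Sensitivity to the assumptions.** Simulated power at n = 171 (6,000 runs each), with a true correlation of about 0.21 in the linear rows and a group difference of 0.54 SD in the step row:

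| Scenario | Continuous | Yes/no |
|---|---|---|
| Normal T-score, linear | 80% | 49% |
| Heavy-tailed, linear | 79% | 47% |
| Left-skewed, linear | 80% | 58% |
| Right-skewed, linear | 80% | 36% |
| Normal T-score, step at the cut | 49% | 79% |

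The loss does not depend on normality, though its size does. It does depend on the relation being graded: under a pure step the order reverses.

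**5. Student's t-test with 34 against 137.** Suppose the smaller group's SD is 1.5 times the larger group's. The true variance of the difference is 2.25/34 + 1/137 = 0.0735. The pooled test uses [(33 × 2.25 + 136)/169] × (1/34 + 1/137) = 1.244 × 0.0367 = 0.0457. The ratio is 1.61, with square root 1.27, so the critical value 1.974 acts like 1.974/1.27 = 1.56 and the false-positive rate is about 12%. Simulation agrees (Student about 12%, Welch about 5%). At an SD ratio of 1.25 Student's simulated rate is 8.5%; with equal SDs both tests are at about 5%.

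**The case against.** The strongest reply is that section 10 already relates bone to the heart without a split. The bone formation marker regression is named as the test of the primary hypotheses, and the exploratory aims are worded in terms of bone metabolism. This stands as far as it goes: a reader might infer that bone enters the cardiac analyses only as a dichotomy, and that is not so. But a formation marker measures turnover, not density, so the gap for density remains.

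Second, osteoporosis is the diagnosis behind the primary aim, and whether cardiac measures differ by diagnosis is a legitimate question. This also stands. It is a reason to keep the yes/no ANCOVA, not a reason to omit the continuous analysis.

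Third, the documents give neither the shape of the relation nor the distribution of the T-score, and a threshold would favour the planned coding. This stands too, so the loss must be stated with its condition.

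Fourth, the 1.5-fold SD ratio is hypothetical, and section 10 leaves the choice of test open with an as-appropriate clause. That is fair, although Welch's test is not among the options listed. The point about the t-test is therefore only a minor option.

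Finally, the study was not sized for these comparisons. That limits the priority of the change, but data already collected can still be used more efficiently.

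**Conclusion.** The point holds for DXA bone density. Its relation to echocardiographic and other variables is planned only through osteoporosis yes/no, and no continuous T-score or BMD analysis is described. For a roughly normal T-score and a linear relation, this costs about 51% of the information on that association at 20% prevalence (45% to 59% over 14% to 26%). At a correlation of 0.20, power is about 45% where about 75% was available.

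Three stronger readings are not supported:

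- That half the information in the sample is lost. The loss concerns one association under a stated shape. The prevalence, fracture, blood pressure, stiffness and bone-marker analyses lose nothing, and the prevalence aim needs the yes/no definition.
- That a null yes/no result would be uninformative. A contrast able to detect 0.54 SD with 80% power still yields an interpretable confidence interval.
- That the t-test is shown to be invalid. The inflation appears only under an assumed SD difference.

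This is a worthwhile, inexpensive improvement to exploratory analyses and not a flaw that invalidates a planned result.

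**What to change.** In section 10, add the T-score or BMD at one site named in advance (for example the femoral neck) as a continuous predictor of each echocardiographic and other continuous outcome. Express it per 1 SD, fit it linearly with a check for curvature, and use the same covariates as the planned ANCOVA. Keep the osteoporosis yes/no ANCOVA alongside it. Naming the site now matters because several are scanned, and choosing among them later would add an unplanned selection. Stating both codings now also prevents a choice between them after the results are seen.

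Optionally, replace Student's t-test with Welch's for the unadjusted comparison of these unequal groups.

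The cost is a sentence or two of text and one extra model per outcome, with no new data, visits or patients. The downside is that a linear term can miss a pure threshold effect; the retained yes/no contrast covers that case.

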## 11. Data processing

All generated data will be recorded in case report forms (CRF) and will be transcribed into Excel or SPSS datasets. In electronic datasets participating subjects can only be identified by their unique study ID, name and surname will not be recorded.

## 12. Data access

All CIs will have unlimited access to the dataset.

## 13. Responsibilities and competences

Only the principal investigators ([name], [name]) will have unlimited access to study data and will have the right to nominate co-authorships and the position of co-authors, on publications that originate from data of the RoC-HF study. Forwarding of anonymized RoC-HF data may only occur with permission of both the PIs.

